The intervention group will receive Ketamine, while the placebo group will have an identical syringe of normal saline prepared. The placebo will be prepared to blind the cardiac anesthetist caring for the patient. This blinding is important as the quantity of narcotic administered during the surgery is at the anesthetist's discretion, and knowing whether or not a co-analgesic is being administered may affect the quantity of narcotic administered. The quantity of narcotic administered could be considered a co-intervention of the primary outcome, so we are taking all precautions to ensure that the amount of narcotic administered is not influenced by the anesthesiologist's knowledge of the study drug.

The cardiac anesthesiologist will receive the medication in the operating room, delivering a bolus prior to skin incision and administering the medication at a rate determined by the patient's weight. The dose of medication administered should not have any hemodynamic effects, and so unblinding of the cardiac anesthetist should not be necessary. If, for whatever reason unblinding should become necessary, the co-investigator who prepared the medication will make the primary anesthetist aware of the contents of the study drug.

Upon transfer to the intensive care unit, nurses and intensive care physicians will be made aware that the patient is involved in the study. The research coordinator will have documented the volume of study drug administered in the anesthetic record at the end of the

case. If the treatment allocation needs to be known by the intensive care team, they will be able to contact the primary investigator to be immediately unblinded.

Patients will be asked if they would allow the research coordinator to call them at 3 and 6 months after surgery to ask if any pain is present at the site of incision, followed by ten yes or no questions about the pain, and what medications they may be taking for pain, if the pain is still present. These questions can be found in the attached questionnaire.¹⁴

Study Population

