The study population will be patients coming for CABG surgery via midline sternotomy at the Jewish General Hospital. This population was selected to ensure all patients have a similar incision and number of chest tubes, two of the main contributing factors to postoperative pain. Patients with a left ventricular ejection fraction less than 50% will be excluded, as these patients are more likely to require a longer duration of circulatory support and mechanical ventilation. Extended mechanical ventilation and sedation will make it difficult to assess the primary outcome of the study. Patients with a history of regular opioid use will be excluded, as these patients have an increased tolerance to opioids and require larger doses to achieve adequate pain control. Including these patients in a small randomized study would risk having a significant effect on the primary outcome. Patients with known hepatic or renal dysfunction will be excluded as well, given the theoretical accumulation of ketamine. Patients with a contraindication to ketamine will also be excluded, such as those with a previous cerebrovascular accident, or with known hypersensitivity to the drug. Patients unable to

provide consent will also be excluded, as the reporting of pain in these patients will likely be unreliable.

Exposure

Exposure will be randomized to an intervention or placebo. The intervention arm will consist of ketamine as a 0.5mg/kg as a bolus, and a 0.5mg/kg/hr infusion throughout the surgery. For an 80kg patient, with a Ketamine concentration of 10mg/mL, this would amount to a 2mL bolus and 2mL of fluid administration per hour of surgery, or approximately 10mL of fluid for the duration of a surgery. The placebo arm will consist of a saline infusion at the same volumes. This dose of ketamine is based on previous studies that have shown effectiveness in surgical populations. The doses at which Ketamine will be administered is not expected to have any hemodynamic effects, and therefore compliance by the anesthesiologist with the treatment is be expected to be near 100%.

Both treatment arms will receive a full cardiac anesthetic in addition to the study intervention. Since the total quantity of intraoperative opioids administered will depend on infusion rate and duration of anesthesia, the total dose administered will be noted for each patient.

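### The worked volume example for ketamine gives exactly half of the stated dose at the stated concentration

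*Combined protocol and SAP*

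**What the plan says.** The Exposure section defines the active arm as "ketamine as a 0.5mg/kg as a bolus, and a 0.5mg/kg/hr infusion throughout the surgery". The next sentence turns this into volumes: "For an 80kg patient, with a Ketamine concentration of 10mg/mL, this would amount to a 2mL bolus and 2mL of fluid administration per hour". That sentence ends with a total: "or approximately 10mL of fluid for the duration of a surgery". Placebo is saline in matching volumes. The section then supports the regimen by reference to earlier work: "This dose of ketamine is based on previous studies that have shown effectiveness in surgical populations".

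The Study Design section has a co-investigator prepare the syringe and a blinded cardiac anesthesiologist give it, the latter "administering the medication at a rate determined by the patient's weight". On records, it says: "The research coordinator will have documented the volume of study drug administered in the anesthetic record". No other part of the document gives a concentration, a volume or a different dose for the study drug.

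**The concern.** The dose, the body weight, the concentration and the resulting volumes appear in two adjacent sentences and do not agree. One of them must be wrong, and the document does not say which.

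The disagreement matters because of how the drug is handled. One person prepares it, a second person who is blinded gives it from a syringe that looks the same in both arms, placebo is matched by volume, and volume is what is recorded. Preparer and anesthesiologist therefore need one agreed concentration and one agreed set of volumes, and the only text linking the two is the example.

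If staff scaled from it, the active arm would receive half the stated dose. A trial sized to detect a 25% reduction in opioid use could then be testing a weaker intervention than the one described, and a reader could not tell which regimen the result applies to. The documents contain no dose-response information, so the loss of effect cannot be put into numbers.

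**Working it through.** **Inputs, all from the Exposure section:** bolus 0.5 mg/kg; infusion 0.5 mg/kg/hr; example weight 80 kg; concentration 10 mg/mL; stated volumes 2 mL, 2 mL/h and about 10 mL in total.

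**Step 1. Try to reproduce the stated volumes.** Volume = dose (mg/kg) × weight (kg) ÷ concentration (mg/mL).

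- Bolus: 0.5 × 80 = 40 mg; 40 ÷ 10 = 4 mL (stated: 2 mL).
- Infusion: 0.5 × 80 = 40 mg/h; 40 ÷ 10 = 4 mL/h (stated: 2 mL/h).

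The stated figures are not reproduced.

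**Step 2. What the stated volumes would deliver.** 2 mL × 10 mg/mL = 20 mg; 20 ÷ 80 = 0.25 mg/kg. The same calculation gives 0.25 mg/kg/hr for the infusion.

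**Step 3. Is it a single stray digit?** The document gives no duration of surgery. Solving 2 + 2T = 10 gives T = 4 h, a whole number, so the bolus, the rate and the total agree with one another. The halving runs through the whole example.

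**Step 4. Other weights.** The stated dose is 0.5 ÷ 10 = 0.05 mL/kg. The example is 2 ÷ 80 = 0.025 mL/kg. The ratio is 0.05 ÷ 0.025 = 2 at every weight.

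| Weight | Bolus (and mL per hour) from stated dose | Scaled from example |
|---|---|---|
| 60 kg | 3.0 | 1.5 |
| 80 kg | 4.0 | 2.0 |
| 100 kg | 5.0 | 2.5 |

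**Step 5. Total at 80 kg over T hours.** The stated dose gives 4 + 4T mL and the example gives 2 + 2T mL. The ratio is 2 for every T.

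| T | From stated dose | From example |
|---|---|---|
| 3 h | 16 mL | 8 mL |
| 4 h (implied) | 20 mL (200 mg) | 10 mL (100 mg) |
| 5 h | 24 mL | 12 mL |

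**Step 6. What would reconcile the sentences?** A 2 mL bolus is right if the concentration is 40 mg ÷ 2 mL = 20 mg/mL, or if the dose is 0.25 mg/kg, or if the patient weighs 2 × 10 ÷ 0.5 = 40 kg. The document states none of these.

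**The case against.** The arithmetic is not open to dispute, so the case on the other side is about consequence. The dose is stated explicitly in mg/kg and mg/kg/hr, and the volumes only illustrate it. A physician who calculates from dose, weight and concentration arrives at 4 mL without consulting the example. The Study Design section speaks only of a rate set by weight; it does not tell anyone to scale in mL/kg from the illustration. If the example were followed, the error would be towards too little drug, not too much. Placebo matching, blinding, randomization, the analysis and the sample size calculation do not depend on these volumes.

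All of that stands, and it keeps the point well short of a fatal flaw. It does not remove the contradiction, because the example is the document's only conversion to volume in a trial that prepares, matches and records study drug by volume.

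Two further cautions also stand. The sentence appealing to earlier studies names no figure. Reading it as support for 0.5 mg/kg is natural, but it cannot be confirmed from the document. Also, the recorded volume alone does not give the dose in mg/kg and mg/kg/hr. That needs the concentration prepared, the patient's weight, the infusion time and the split between bolus and infusion, and the document does not say that the two are recorded separately.

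**Conclusion.** The concern holds. The example is wrong as written, by exactly a factor of two in the bolus and the hourly rate, and likewise in the total for any given duration. The factor depends only on the protocol's own dose, weight and concentration. The absolute totals rest on a duration of about 4 h, which is inferred from the stated 10 mL.

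The document does not settle whether the volumes, the concentration or the dose is in error. The volumes are the likeliest, since the mg/kg regimen is the explicit specification. Whether any patient received half the dose cannot be known from the document. It should be corrected because it concerns the dose of the experimental treatment.

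**What to change.** Correct the sentence in the Exposure section according to what was intended:

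- If 0.5 mg/kg and 0.5 mg/kg/hr at 10 mg/mL are intended, state a 4 mL bolus, 4 mL/h, and about 20 mL for a surgery of about 4 h.
- If the volumes are intended with the stated dose, change the concentration to 20 mg/mL.
- If the volumes and 10 mg/mL are both intended, change the dose to 0.25 mg/kg and 0.25 mg/kg/hr, and check that the supporting studies cover it.

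State the volumes per kilogram, and apply the same ones to saline. If patients have already been treated, establish the dose given from the recorded study-drug volumes, the concentration actually prepared, patient weight and infusion duration, and report it.

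The cost is one sentence, with no extra patients or procedures. The retrospective check, if needed, is a review of existing records.

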Postoperative opioids will be prescribed at a dose and frequency according to the standard postoperative orders for cardiac surgery patients. An intensive care nurse will administer opioids at the doses prescribed on the post-operative orders. This strict protocol for pain management improves the internal validity of the trial, understanding that this may

somewhat decrease external validity in comparison to other centers who do not manage postoperative pain with the same regimen.

Outcomes

The primary outcome is the quantity of opioid administered over the first 48 hours postoperatively. Forty-eight hours was selected as the duration to monitor opioid consumption, as this is the period during which pain post-cardiac surgery has been shown to be most intense. This primary outcome was selected as it will be reliably documented and straightforward to assess, given the strict guidelines for documentation of opioids.

There will be several secondary outcomes. The quantity of opioids used at 24 hours will be noted. Postoperative pain will be measured daily via the "brief pain inventory" by the research coordinator on postoperative days 0, 1, and 2.¹³ Patients will be asked their current pain, the worst and best pain levels throughout the day, as well as their average pain levels. The need for additional analgesic medications will be assessed as a binary outcome for each type of additional medication (NSAIDs, additional opioids, gabapentinoids, etc), measuring whether or not additional agents are added to treat poorly controlled pain. Additional analgesics would likely affect the dose of post-operative opioids administered, making it a co-intervention which may need to be accounted for in the analysis. The presence or absence of postoperative nausea and vomiting requiring treatment, as well as the diagnosis of delirium will be measured as binary outcomes. Intensive care unit and hospital length of stay will be measured in number of days, while the time to extubation, time to first mobilization to a chair, and time to first ambulation will be measured in number of hours after arrival to the intensive care unit through

chart review. While the dose of ketamine used in this study is not likely to cause psychological side effects, the number of patients reporting hallucinations or severe nightmares will be tracked.

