On follow-up phone call at 3 and 6 months patients will be asked whether or not they have persistent pain at the site of the sternotomy. Whether or not persistent pain is present will be noted, along with any medications that they may be taking for the pain. If persistent pain is present, they will be asked ten yes or no descriptive questions about the pain concerning to determine if it is neuropathic in origin.¹⁴ The answer to each question, as well as the overall score will be noted.

Confounders

Possible baseline confounders will be tracked to look for differential distribution between intervention groups. These will include age, sex, body mass index, left internal mammary harvesting. We will stratify our randomization by sex to ensure sexes are balanced in the 2 groups, as sex has been shown to be one of the main confounders for postoperative pain. With a relatively small sample size of 80 patients, a differential distribution of confounders between groups is possible, and an adjustment will be done in our analysis for any factor that is differentially distributed. Injuries during cardiac surgery such as rib fracture and dislocation, or fractured sternum may contribute to postoperative pain as well. Unfortunately, these variables often go undetected and cannot be adequately tracked. We will therefore rely on randomization to ensure equal distribution in both groups.

Analysis Plan

While nearly complete compliance is expected with the therapy, an intention-to-treat analysis will be performed in case any unforeseen issues with compliance arise during the study. Continuous data such as postoperative opioid dose, intensive care unit and hospital length of stay, and time to mobilization and ambulation will be evaluated using the t test if it is determined that the means are normally distributed, or the Wilcoxon Rank Sum test if the means are not normally distributed. Ordinal data such as visual analog scale scores and binary data such as need for additional analgesics and the presence or absence of PONV will be evaluated by a Chi-Square test. If confounding is suspected due to baseline differences in the variables noted above, we will perform a propensity score depending on the variable(s) and the size of the difference. As a secondary analysis, data will be analyzed in subgroups by sex to look for any potential difference in response.

Sample Size & Power Analysis

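### Acute pain yields 12 scores per patient, with no named pain endpoint and no analysis that uses a patient's repeated scores together

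*Combined protocol and SAP*

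**What the plan says.** The Outcomes section names one primary outcome: "The primary outcome is the quantity of opioid administered over the first 48 hours postoperatively". It then says "There will be several secondary outcomes", and acute pain is among these. Pain is measured with the brief pain inventory "by the research coordinator on postoperative days 0, 1, and 2", and "Patients will be asked their current pain, the worst and best pain levels throughout the day, as well as their average pain levels". That is four ratings on three days. The section does not single out any rating, day, average or composite.

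The only rule in the Analysis Plan that could cover these ratings is this: "Ordinal data such as visual analog scale scores and binary data such as need for additional analgesics" (together with postoperative nausea and vomiting) "will be evaluated by a Chi-Square test". The plan contains no repeated-measures model, summary score, ordering of outcomes or multiplicity rule. The Outcomes section does not mention a visual analog scale, so the instrument actually used is not tied to an analysis by name. The same section adds: "As a secondary analysis, data will be analyzed in subgroups by sex to look for any potential difference in response".

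**The concern.** The specific aim is whether ketamine improves pain control after surgery, and the primary outcome measures this indirectly, through opioid quantity. The protocol's own limitations note that patients differ in when they ask for analgesia and nurses in when they give it. The in-hospital ratings are therefore needed to interpret an opioid difference: less opioid with equal or lower pain is a benefit, and less opioid with more pain is not.

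With 12 scores and no named lead, that interpretation can be chosen after the data are seen. Two things are at stake. One is a raised chance that some score differs between arms by luck. The other is lost precision, because a test on a single day ignores the patient's other days. A pilot should hand the next trial one clear pain estimate with an interval, and this plan does not say which estimate that would be.

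**Working it through.** **The plan's own figure.** The documents give no SD, error rate or power for the pain scores. The only sample-size figures, in Sample Size & Power Analysis, concern opioid quantity: a 25% fall from 125 mg is 31.25 mg, SD 45 mg, standardised effect 31.25/45 = 0.694. A two-sided 5% t-test needs 33.5 per arm for 80% power and 44.6 for 90%, which round up to the stated 34 and 45. With 40 per arm the power is 86.6%, in line with the stated power of over 80%. Those figures stand, and nothing below changes them.

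**Number of scores.** 4 ratings × 3 days = 12 per patient.

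**Chance of at least one p<0.05 with no true effect.**
- If the 12 tests were independent: 1 − 0.95^12 = 46.0%. This is an upper reference, since scores from the same patient are positively correlated.
- With correlation, 12 two-sided z tests were simulated from a multivariate normal distribution (400,000 draws). The correlation between two scores was the item correlation times the day correlation. The documents give neither, so both are assumed:

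| Item correlation | Day correlation | P(at least one p<0.05) |
|---|---|---|
| 0.5 | 0.3 | 38% |
| 0.6 | 0.5 | 33% |
| 0.8 | 0.6 | 25% |
| 0.9 | 0.7 | just under 20% |

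The first three rows give the 25-38% range, about 5 to 8 times the nominal 5%. These are tests with exact 5% size. The unordered chi-square test is slightly conservative: simulated on an assumed 0-10 scale (mean 4.5, SD 2.2, 40 per arm), its size was 3.6%. Twelve independent tests at that size give 1 − 0.964^12 = 36%.

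**Precision from using several days.** For one rating with day-to-day correlation r, the variance of a mean relative to one day is (1 + r)/2 for two days and (1 + 2r)/3 for three. The effect is assumed to be 0.5 SD of a single day's score, the same on every day. Dividing 0.5 by the square root of the variance ratio gives the standardised effect for a t-test with 40 per arm:

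| r (assumed) | Variance ratio, 2 days | Power, 2 days | Variance ratio, 3 days | Power, 3 days |
|---|---|---|---|---|
| 0.3 | 0.65 | 78% | 0.53 | 86% |
| 0.5 | 0.75 | 72% | 0.67 | 77% |
| 0.7 | 0.85 | 67% | 0.80 | 69% |

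A t-test on one day has 60% power (59.8%). The plan's chi-square test on one day has less: in the same 0-10 simulation, a 0.5 SD shift gave about 17%.

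**The case against.** The strongest reply is that these are secondary outcomes in a self-described pilot. The protocol states its hypothesis in terms of opioid consumption, names one primary outcome and sizes the trial on it alone. Leaving secondary outcomes unranked and unadjusted is common in pilots. This stands as a limit on importance: the primary result is not at risk. It does not answer the missing pain endpoint or the lost precision.

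Four stronger readings are tempting, and the documents do not support them.
- A reader might infer that a chance pain difference is likely. The range is 25-38%, and even full independence gives 46%. If every score were also tested within each sex (36 comparisons, women assumed to be 20-30%), the figure would be 45-67% under assumed correlations. The subgroup sentence, however, does not say that the pain ratings will be repeated by sex.
- A reader might take 12 separate tests as the stated plan. They are inferred from the absence of any other analysis.
- A reader might call the ratings the only direct measure of pain. The protocol also asks about persistent sternotomy pain at 3 and 6 months, so the ratings are the direct measure of acute pain only.
- A reader might take 60% as the plan's own power for one day. That figure is for a t-test, whereas the plan names chi-square. Part of any gain over the plan would therefore come from changing the test, which is a separate matter from pooling days.

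The visual analog scale wording is a small point. It is offered as an example of ordinal data, so the inventory ratings plausibly fall under the same rule, and the mismatch is one of naming.

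**Conclusion.** The point holds in a limited form. The plan collects 12 acute pain scores per patient, does not say which is the pain result, and has no analysis that uses a patient's days together. If the scores are tested one by one, the chance of a spurious difference in at least one is roughly one in four to nearly two in five, rather than 5%. Pooling days would raise power for a constant 0.5 SD effect by about 7 to 26 percentage points over a t-test on a single day (from 60% to between 67% and 86%).

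The item and day correlations, the effect size and its constancy over days, and the 0-10 scale are all assumptions. The size of the problem moves with them, but the gap in the plan does not. It bears on how the secondary pain result is reported and leaves the validity of the primary comparison untouched.

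**What to change.** Before unblinding, amend the Outcomes section and Analysis Plan as follows:
- Name one brief pain inventory rating as the acute pain endpoint. Average pain is one example, and another choice is acceptable if a reason is given.
- Analyse that rating across the assessed days, either in one repeated-measures mixed model (arm, day, arm by day) or as a patient-level mean compared between arms. Report one arm difference averaged over days, with a 95% CI.
- State which days enter the endpoint, and give a reason if day 0 is left out.
- Report the other ratings descriptively, without p-values.
- Replace the reference to visual analog scale scores with brief pain inventory ratings.

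The cost is a few lines of text and one model, with no new data. The downside is that the other pain ratings lose their p-values.

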Pilot Study: The Effect of Intraoperative Ketamine on Analgesia Post-Cardiac Surgery and Prevention of Postoperative Pain

JGH Protocol #: 16-289 NCT02925858

Primary Investigator: [name]

Co-Investigator: [name] [name]

Co-Investigator: [name]

Co-Investigator: [name] [name]

Co-Investigator: [name]

Background

Pain control post-sternotomy is an essential part of fast-track surgery, a program to promote early recovery. Up to 75% of patients complain of moderate-to-severe pain after cardiac surgery, with poorly controlled pain leading to an increased risk of myocardial ischemia and chronic post-sternotomy pain, which is seen in 11% of patients. Given the relative contraindications to epidural analgesia and non-steroidal anti-inflammatories after coronary artery bypass grafting (CABG) surgery, options for multimodal analgesia are limited.

Ketamine is an NMDA antagonist which potentiates the release of inhibitory neurotransmitters, modulating the sensory processing of pain.⁴ Ketamine is a well-established treatment for a variety of pain syndromes, and is approved by Health Canada to be used as a supplemental agent during anesthesia.⁵⁻⁷ There is a growing literature showing that Ketamine contributes to pain control after surgery as well. It has been shown that Ketamine decreases opioid needs after spine surgery, as well as after thoractomy.⁸⁻¹⁰ While these studies used the racemic form of Ketamine, the only version approved for use in Canada, a Finnish study on the cardiac surgery population evaluated the S(+) enantiomer of Ketamine, which has not been available in Canada. This was shown to reduce postoperative opioid requirements by 20%.¹¹

There are limited downsides to the administration of Ketamine. The most common adverse effects of ketamine in awake patients include nightmares, hallucinations, a dissociative state, headaches, and hepatotoxicity. ^{5,12} In clinical studies of low dose Ketamine used for perioperative pain control, there has not been shown to be a significant increase in side effects between treatment and placebo groups. ⁹

Ketamine, while used at times, is not routinely used during cardiac anesthetics. It has not been studied for its effect on postoperative pain control and its effect on post-sternotomy chronic pain.

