Given that the S(+) enantiomer of Ketamine previously studied in cardiac surgery patients is not available in Canada, this study will investigate the racemic form of Ketamine that is available in Canada, which, to our knowledge, has not been studied in the cardiac surgery population. This is the form of ketamine will has well established use during anesthesia care and the form of ketamine with which the vast majority of the literature on postoperative pain has been based.

Specific Aim & Hypothesis

The main goal of this pilot study is to assess the effect of an intraoperative intervention, the administration of ketamine, on analgesia post-cardiac surgery. This pilot study will also help assess the feasibility of recruiting and retaining patients, safely administering a blinded medication in the operating room, accurately measuring a primary outcome of postoperative narcotic consumption, and blinding those involved in the care of cardiac surgery patients.

The long-term goal of this study and subsequent follow-up studies is to improve pain control after cardiac surgery, with the hope of allowing patients to perform earlier physiotherapy, regain functional status, and allow for an earlier discharge from hospital.

The specific aim of this study is to ascertain whether an intraoperative infusion of racemic Ketamine can improve postoperative pain control after CABG surgery. The hypothesis is that the intraoperative administration of this medication will improve postoperative pain

control demonstrated through a decrease in postoperative opioid consumption of more than 25%.

Study Design

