Using the data in the trial evaluating S(+)-Ketamine, an estimate of 125mg of oxycodone over the 48 hours post cardiac surgery was used as a baseline.¹ In this same study, both the intervention and controls groups had standard deviation of oxycodone of 45mg. To detect a decrease in opioid requirements of 25% with a power of 80% and a two-sided alpha of 0.05, a total of 68 patients would be required in the trial, with 34 in each group. For a power of 90%, a total of 90 patients would be required in the trial with 45 patients in each arm. The Jewish General Hospital, a McGill University teaching hospital, performs approximately 600 cardiac surgeries per year, with approximately 350 CABG surgeries via sternotomy. The goal will be to

enroll 80 patients. With the nature of this study and the need for hospitalization post-cardiac surgery, there should be minimal, if any, drop-outs or loss to follow-up, and therefore the sample size of 80 patients should allow for a power of over 80%.

Strengths & Limitations

Strengths of the study include the ability to randomize, and the ability to blind the patients, nurses, anesthesiologists and pain evaluators. This study will be performed at a single center, which allows for easier standardization of therapy, at the same time limiting generalizability of the findings. The primary outcome, opioid use, is easily measurable.

Limitations will include the inter-individual variability in both patient thresholds for analgesia request, and nurse thresholds to administer analgesia. Injury during cardiac surgery may contribute to pain (rib fracture or dislocation), and will not be able to be accurately measured.

Timetable

The Jewish General Hospital currently performs approximately 350 CABG surgeries per year, which is approximately 30 per month. Once ethics approval is obtained, and organizational logistics are arranged, the goal would be to recruit 80 patients over the span of four months. Another 2 to 3 months will likely be required for full data analysis and manuscript preparation.

References

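### Of the five ketamine adverse effects the protocol lists, dissociation, headache and liver toxicity have no stated collection and nightmares count only if severe, so the pilot's tolerability data would be partial

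*Combined protocol and SAP*

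**What the plan says.** The Background states: "The most common adverse effects of ketamine in awake patients include nightmares, hallucinations, a dissociative state, headaches, and hepatotoxicity". It then adds that in clinical studies of low-dose perioperative use "there has not been shown to be a significant increase in side effects between treatment and placebo groups".

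Among the matters whose feasibility the pilot will assess, the Specific Aim & Hypothesis section includes "safely administering a blinded medication in the operating room".

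The Outcomes section, after remarking that psychological side effects are unlikely at this dose, says that "the number of patients reporting hallucinations or severe nightmares will be tracked". The same section also collects two other events relevant to tolerability: "The presence or absence of postoperative nausea and vomiting requiring treatment, as well as the diagnosis of delirium will be measured as binary outcomes".

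The liver appears once more, as an entry criterion in Study Population: "Patients with known hepatic or renal dysfunction will be excluded as well, given the theoretical accumulation of ketamine". No liver assessment after dosing is described.

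**The concern.** The protocol names the effects it regards as most common and makes safe administration something the pilot should inform. It then plans to count fewer than half of those effects. Dissociative state, headache and hepatotoxicity have no place in the data, and a nightmare counts only if it is severe, a term the protocol does not define. For the two effects that are counted, no time window, assessor or question is given, so one reader could plan direct questioning and another could wait for complaints. These two methods can give very different counts.

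The stake is limited. The pilot is meant to lead to follow-up studies, and its side-effect counts are among the things those studies would use. A partial list, gathered by an unstated method, gives them little to plan on and makes comparison with other trials difficult.

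**Working it through.** **Listed effects against planned collection**

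| Effect listed in Background | Collected under Outcomes? |
|---|---|
| Hallucinations | Yes, method not stated |
| Nightmares | Only if severe, method not stated |
| Dissociative state | No |
| Headache | No |
| Hepatotoxicity | No (hepatic dysfunction is an exclusion at entry only) |

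Two of five are covered, one of them in part; three of five are not. Adding treated nausea and vomiting and diagnosed delirium, four binary events relevant to tolerability are collected in all.

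Could another planned item pick up the missing effects?
- The daily pain inventory asks for current, worst, best and average pain. No site is mentioned, so a headache would not be identifiable as one.
- A delirium diagnosis may overlap clinically with dissociation, but it is not a count of dissociative symptoms.
- The text describes no general adverse-event record that would catch the rest.

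**Arm size, and whether the plan's sample size is touched**

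Inputs from Sample Size & Power Analysis: "an estimate of 125mg of oxycodone over the 48 hours post cardiac surgery was used as a baseline", SD 45 mg in both groups, 25% reduction, two-sided alpha 0.05.
- Difference: 0.25 × 125 = 31.25 mg. Standardised: 31.25 / 45 = 0.694.
- Two-sample t test, 80% power: 33.5, rounded up to 34 per arm. The plan says 34.
- At 90% power: 44.6, rounded up to 45 per arm. The plan says 45.
- With 80 enrolled, 80 / 2 = 40 per arm, and power is 86.6%, consistent with the plan's claim of over 80%.

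The plan's figures reproduce, and nothing in this point alters them.

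**What 40 ketamine patients can say about an effect that is recorded**

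Upper limit when no events are seen in n patients: 1 − a^(1/n).
- One-sided 95%: 1 − 0.05^(1/40) = 0.072, or 7.2%.
- Upper end of the exact two-sided 95% interval: 1 − 0.025^(1/40) = 0.088, or 8.8%.

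Chance of seeing at least one event in 40: 1 − (1 − p)^40. The rates p are assumptions, since the documents give none.

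| Assumed true rate | Chance of at least one event |
|---|---|
| 1% | 33% |
| 2% | 55% |
| 5% | 87% |
| 10% | 98.5% |

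Approximate 95% half-width for a between-arm difference, if the rate were 10% in each arm (again an assumption): 1.96 × √(2 × 0.10 × 0.90 / 40) = 1.96 × 0.067 = 0.13, or 13 percentage points.

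So the recorded effects would be estimated only roughly, and the unrecorded ones not at all.

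**The case against.** The best defence is that the short list is deliberate. The five effects are described for awake patients, whereas here the drug is given during surgery on top of a full cardiac anesthetic. The Background cites low-dose studies showing no significant excess of side effects, and the Outcomes section repeats the expectation for psychological effects. The safety objective is worded for the operating room, and mild nightmares or headache on the ward bear little on it.

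Much of this stands, and it is why the point is minor. It does not close the gap. The planned counts rely on patients who are awake enough to report symptoms after surgery. Absence of a significant increase elsewhere does not show absence of the effects, and the protocol itself says that, to the authors' knowledge, racemic ketamine has not been studied in cardiac surgery patients. The remark about psychological effects does not address headache or the liver.

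Three stronger readings are tempting and are not supported:
- A reader might infer that hallucinations and severe nightmares are the whole of the safety tracking. They are not: treated nausea and vomiting and diagnosed delirium are measured too.
- A reader might infer from the verb used for these symptoms that they are counted only when volunteered. The protocol does not say. A coordinator who sees the patient on three days could equally well ask.
- A reader might infer that the pilot will issue a safety conclusion inflated by the partial list. No section promises such a conclusion.

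**Conclusion.** The point holds in a limited form. Among the five effects the protocol itself lists, three have no stated collection and a fourth is collected only when severe, and the way symptoms are elicited is left open. The primary outcome, the sample size and the main analysis are untouched. What is lost is part of the tolerability information for later studies: with 40 assessed and no events, a recorded effect would still be bounded only at 8.8% (two-sided) or 7.2% (one-sided), and an unrecorded effect has no bound.

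This rests on about 40 ketamine patients all being assessed, and on the protocol text available; pages removed from it, such as consent material, cannot be checked. It does not imply that any of these effects is expected at the planned dose. The change is worth making because it is nearly free, not because the trial is compromised without it.

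**What to change.** At the coordinator's existing pain visits on days 0, 1 and 2, once the patient can respond, put the same yes/no questions to every patient in both arms:
- nightmares (any; severe)
- hallucinations
- dissociative feelings
- headache

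Ask them after the pain scores, so that the answers do not colour the pain rating. Record at each visit whether the patient could be assessed. Report counts by arm with the number assessed and exact 95% intervals, as description rather than as a test of safety.

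Liver effects cannot be handled in this way. The documents do not say that liver tests are routine, and results found in charts would come from an unknown and selected subset. At most, list such results descriptively with the number tested, and do not present them as a rate. It would also help to say plainly in the protocol that hepatotoxicity is not being assessed as an outcome.

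The cost is a few added questions at visits that already take place, with no extra staff, visit or test. The downside is that prompting raises counts in both arms. Because patients and the coordinator are meant to be blinded, the between-arm difference remains interpretable, and it is this, rather than the absolute rate, that should be read.
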